1.0 Objectives

1.1 Describe the purpose, specific aims, or objectives of this research.

Response: To study the effects of transcranial direct current stimulation (tDCS) on weight and appetite.

Aim:

- 1. To compare weight loss over one month in active tDCS group with sham tDCS group. We will measure weight of every participants at the beginning of the study and one month after the last session of tDCS*
- 2. To compare change in insulin sensitivity over one month in active tDCS group with sham tDCS group. We will measure fasting insulin and glucose level, and calculate homeostatic model assessment-insulin resistance (HOMA-IR)*
- 3. To compare change in cognitive performance as a response to food over one month in active tDCS group with sham tDCS group. We will evaluate performance in a computerized task that measures executive functions under the presence of food (working memory, inhibitory control and a combination of both). We will assess changes in accuracy and speed in the task under active tDCS versus sham tDCS.*
- 4. To compare change in post-prandial glucose excursion and average meal counts per day. We will use continuous glucose monitor to record the frequency and amplitude of glucose excursion.*

1.2 State the hypotheses to be tested, if applicable.

NOTE: A hypothesis is a specific, testable prediction about what you expect to happen in your study that corresponds with your above listed objectives.

Response:

Hypothesis:

- 1. Active tDCS will result in more weight loss, appetite reduction and improved insulin sensitivity compared with sham tDCS over one month period.*
- 2. The effect of tDCS on weight, appetite, glucose tolerance and cognitive response to food varies according to the underlying allele status of BDNF and COMT gene*

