2.0 Scientific Endpoints

2.1 Describe the scientific endpoint(s), the main result or occurrence under study.

*NOTE: Scientific endpoints are outcomes defined before the study begins to determine whether the objectives of the study have been met and to draw conclusions from the data. Include primary and secondary endpoints. Some example endpoints are: reduction of symptoms, improvement in quality of life, or survival. Your response should **not** be a date.*

Response:

Primary endpoints: change in weight, measured as a percentage of baseline body weight.

Secondary endpoints: change in HOMA-IR, change in average daily meal counts based on frequency of glucose excursion on continuous glucose monitor, change in average amplitude of glucose excursion curve after meals, change in cognitive performance in response to food

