Subjects assigned to sham tDCS group will receive 15 seconds of anodal tDCS delivered with a neuroConnVR DCSTIMULATOR device (neuroConn GmbH, Ilmenau, Germany), at a constant current of 2 mA (with a 30-second ramp at on- and offset) using two sponge electrodes soaked in a sterile 0.9% sodium chloride solution. However, they will stay at the research center for 30 minutes with electrodes on their scalp. Before starting the stimulation, a code will need to be entered into the tDCS machine which will decide whether a sham or active stimulation will be performed by the machine automatically in the next 30 minutes. At the beginning of the study, a code that is associated with either active stimulation or sham stimulation will be assigned to the subject based on the randomization. However, neither the subject or the operator of tDCS machine will know what does the code represent.

Visit 2: Subjects will come back next day to receive the second session of the same intervention.

Visit 3: Subjects will come back next day to receive the third session of the same intervention.

Visit 4: Subjects will come back next day to receive the fourth session of the same intervention.

Visit 5: Subjects will fast overnight (10 hours) and come back next morning at 7 to 7:30 AM to receive the fifth session of the same intervention. We will then measure body mass index, plasma insulin and glucose, appetite and cognitive function in response to food. Continuous glucose monitor will be reinstalled, and subjects will be instructed to wear it and document the time and types of food of every meal for at least 72 hours after this visit and 72 hours before the next visit. Subject will be instructed on how to insert and remove continuous glucose monitor again.

Visit 6: Subjects will fast overnight (10 hours) and come back next morning at 7 to 7:30 AM in 4 weeks after visit 5. We will measure body mass index, plasma insulin and glucose, appetite and cognitive function in response to food again. We will download data from the continuous glucose monitor. We will also ask if the subject believed that he/she received active or sham tDCS.

10.2 Describe what data will be collected.

NOTE: For studies with multiple data collection points or long-term follow up, consider the addition of a schedule or table in your response.

Response:

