We will collect general demographic data regarding years of education, race/ethnicity. We will also administer the three-factor eating questionnaire (Stunkard and Messick, 1985), which measures eating habits and attitudes toward food, weight and dieting, and a personality questionnaire, the Big Five (Costa and McCrae, 1989).

Plasma glucose and insulin level during screening visit, visit 5 and visit 6

COMT and BDNF gene during screening visit

Weight, height and body mass index (BMI) during screening visit, visit 5 and visit 6
Cognitive response to food during screening visit, visit 5 and visit 6.
Average daily meal counts and type of food based on patient report and continuous glucose meter on visit 1 and visit 6

10.3 *List any instruments or measurement tools used to collect data (e.g. questionnaire, interview guide, validated instrument, data collection form).*

Include copies of these documents with your submission.

Response: Please see form for screening visit, form for follow up visit 1, 2, 5 and 6, eating habit questionnaire, personality questionnaire.

Describe any source records that will be used to collect data about subjects (e.g. school records, electronic medical records).

Response: electronic medical records, clinical charts and research files

10.4 *Indicate whether or not **individual** subject results, such as results of investigational diagnostic tests, genetic tests, or incidental findings will be shared with subjects or others (e.g., the subject's primary care physician) and if so, describe how these will be shared.*

Response: Individual participant lab results will be disclosed to the participant upon their request. If the participant requests documentation be shared with another physician, physician office or hospital, the participant must come to the research center to collect said documentation and/or the documentation can be mailed to their given home address.

10.5 *Indicate whether or not **study** results will be shared with subjects or others, and if so, describe how these will be shared.*

Response: Study results will not be shared directly with subjects. However, study results could be published in the form of a manuscript, to an academic journal.

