17.0 Data Management and Analysis

17.1 Describe the data analysis plan, including any statistical procedures. This section applies to both quantitative and qualitative analysis.

Response:

The demographic features of the population and screening lab results will be displayed in tables. Statistical analysis will be conducted using SigmaStat software version 3.1 (SPSS Inc., Chicago, IL). Data will be represented as mean \pm S.E. Sample size cannot be estimated as this is a pilot study. Generalized linear mixed model will be applied to compare the difference in weight, average amplitude of glucose excursion curve, average daily meal count, HOMA-IR, reaction time and percentage correct response in computerized cognitive tests. Predicting variables include time in the study (baseline, visit 5 and visit 6) and type of intervention (active tDCS vs sham). Sensitivity analysis will be performed to evaluate baseline imbalance, outliers, protocol violation, and missing data. The proposed covariants to be evaluated for baseline imbalance includes age, gender, COMT and BDNF gene status, baseline weight, baseline HOMA-IR, baseline average amplitude of glucose excursion curve, baseline average daily meal count, baseline reaction time and percentage correct response.

17.2 If applicable, provide a power analysis.

NOTE: This may not apply to certain types of studies, including chart/records reviews, survey studies, or observational studies. This question is asked to elicit whether the investigator has an adequate sample size to achieve the study objectives and justify a conclusion.

Response: This is a pilot study, so we are not able to estimate sample size. However, previous shorter term study showed a small effect of tDCS on appetite and weight (see reference 9) in nine patients. We consider that by recruiting 20 participants, it will be more likely to detect a significant change, while the total expense will still be within the limit of our fund.

17.3 Describe any procedures that will be used for quality control of collected data.

Response:

Date entered by research staff will be verified by another person independently.

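### Section 17.1 does not define the visit 6 weight comparison: read literally it averages the one-month effect with earlier visits, and one way of completing the model can understate the visit 6 standard error

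*Combined protocol and SAP*

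**What the plan says.** Section 17.1 (Data Management and Analysis) is the whole inferential plan for efficacy. Its model sentence begins "Generalized linear mixed model will be applied to compare the difference in weight" and goes on to list the secondary outcomes. The predictors follow: "Predicting variables include time in the study (baseline, visit 5 and visit 6) and type of intervention (active tDCS vs sham"). Nothing is said about random effects, a time-by-arm interaction, which visit carries the primary comparison, the covariance between visits, the estimation method, the degrees of freedom or the significance level. The listed sensitivity analyses cover baseline imbalance, outliers, protocol violation and missing data, but not the covariance.

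Section 2.1 defines the primary endpoint as "change in weight, measured as a percentage of baseline body weight", whereas 17.1 speaks of weight. Aim 1 in section 1.1 measures weight at the start and "one month after the last session of tDCS".

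On timing, section 10.1 has subjects attend on consecutive days up to visit 5, where they "receive the fifth session of the same intervention". For visit 6 they "come back next morning at 7 to 7:30 AM in 4 weeks after visit 5". Section 10.2 lists "Weight, height and body mass index (BMI) during screening visit, visit 5 and visit 6", so baseline weight is taken at screening, and 10.1 allows up to 2 weeks between screening and visit 1.

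**The concern.** Aim 1 is a question about visit 6. The model as written has one treatment term that applies to all visits alike, so it does not answer that question. The estimate is a mixture of visits that includes a weight taken on the day of the fifth session.

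An analyst who notices this will add a time-by-arm term, and must then choose a covariance. A subject intercept with one residual variance is an obvious candidate. It treats every between-visit difference as equally variable. If weight drifts, change over the whole follow-up is more variable than change over either part of it, and the model then assigns visit 6 a standard error that is too small. With 20 subjects and a stated hope in section 17.2 of detecting a significant change, the choice can decide what the trial reports. No planned sensitivity analysis would reveal the problem.

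**Working it through.** The documents state no standard error, significance level or variance of weight change, and the enrolment of 20 is not derived from such figures. There is therefore no plan figure to reproduce.

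**Inputs**
- 20 subjects (section 5.1). 10 per arm is assumed: section 10.1 gives a block size of 10 but no allocation ratio.
- Visit 5 is 4 days after visit 1, and visit 6 is 28 days later, so 32 days after visit 1 (section 10.1). If screening weight is baseline, visit 5 is 4 to 18 days and visit 6 is 32 to 46 days after it.
- Assumed: two-sided 5% level, no dropout.

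**Step 1: the literal model.** With complete data, the arm main effect is the average, over the visits modelled, of the between-arm differences. Take a visit 6 difference of 2.0 points that builds up linearly from visit 1 (an illustration, not a figure from the plan). The visit 5 difference is then 2.0 × 4/32 = 0.25.
- Baseline included as an outcome row: (0 + 0.25 + 2.0)/3 = 0.75.
- Visits 5 and 6 only: (0.25 + 2.0)/2 = 1.125.

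The estimate is about 38% to 56% of the visit 6 effect. There is no dilution only if the full effect is already present at visit 5 and baseline is not an outcome row. In simulation (40,000 trials, random walk with and without noise), the type I error of this main-effect test was 4.6% to 5.2% with t on 18 df and 6.0% to 6.9% with z. The literal model has the wrong target; its error rate is not badly inflated.

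**Step 2: time-by-arm added, random intercept, one residual variance.** Let Vij be the variance of the within-subject difference between visits i and j (0 = baseline). The expected residual variance is (V05 + V06 + V56)/6, so the model takes the variance of the visit 6 change to be (V05 + V06 + V56)/3, when it is really V06:

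SE ratio = √[(V05 + V06 + V56)/(3·V06)]

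The SE is too small whenever V05 + V56 < 2·V06.
- Compound symmetry: all three are equal, so the ratio is 1.
- Pure random walk: V05 + V56 = V06, so the ratio is √(2/3) = 0.816, whatever the visit spacing.
- Random walk plus weighing noise, where e is the noise variance divided by the drift variance over the whole follow-up: ratio = √[(2 + 6e)/(3(1 + 2e))]. For e = 1, √(8/9) = 0.943.
- Individual linear slopes, visit 1 as baseline: √[(4² + 32² + 28²)/(3·32²)] = 0.771. With screening 2 weeks earlier as baseline: √[(18² + 46² + 28²)/(3·46²)] = 0.713.

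Type I error was simulated with 10 per arm and 40,000 to 100,000 trials:

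| Assumed structure | SE too small by | Type I error (t, 36 df) |
|---|---|---|
| Compound symmetry | 0% | 5.0% |
| Random walk + noise, e = 2 | 3.4% | 5.7% |
| Random walk + noise, e = 1 | 5.7% | 6.2% |
| Random walk + noise, e = 0.5 | 8.7% | 7.5% |
| Random walk + noise, e = 0.25 | 11.8% | 8.5% |
| Random walk + noise, e = 0.1 | 15.0% | 9.9% |
| Pure random walk | 18.4% | 11.1% to 11.2% |
| Linear slopes, visit 1 baseline | 22.9% | 13.4% |
| Linear slopes, screening baseline | 28.7% | 16.8% |

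With z in place of t, the pure random walk gives about 12%. As a cross-check, 200 REML mixed-model fits under a random walk gave an SE ratio of 0.818 and 11.5% false positives with z (Monte Carlo SE √(0.115 × 0.885/200), about 2.3 points).

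**Step 3: percent change as outcome, visits 5 and 6 only.** The ratio is √[(1 + V5/V6)/2], where V5 and V6 are the variances of change at each visit. For V5/V6 = 1, 0.5, 0.125 and 0, the SE is too small by 0%, 13%, 25% and 29%, with type I error (z) of 5.0%, 9.0%, 14.2% and 16.6%.

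**Step 4: the direct comparison.** Comparing visit 6 change between arms on 18 df gave 4.9% to 5.2% in every scenario. In the random-walk scenario its interval is wider than the random-intercept one by √1.5 × 2.10/2.03 = 1.27, or 27%.

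**The case against.** The strongest reply is that the plan does not say it will fit a random intercept, so an error rate calculated for that fit belongs to the reviewer and not to the plan. That is right. The documents do not show what the named software would fit by default. Read as written, the model has no visit 6 treatment effect whose standard error could be understated, and its main-effect test holds about 5% with t on 18 df.

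A reader might also infer that the gap between a five-day and a five-week follow-up causes the 18% figure. It does not: under a random walk, equally spaced visits give the same 18%. Spacing matters only under some other structures, such as individual slopes, or where percent change is modelled at visits 5 and 6 alone. Nor is it an error to put both visits in one mixed model.

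Finally, this is a pilot, and weighing noise may be large enough to make the inflation small. Both points stand as limits on size. Neither supplies the missing definition: pilot status explains the absence of a power calculation, but not an undefined primary comparison. Leaving the covariance open also allows it to be chosen after the data are seen.

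**Conclusion.** The point holds as an under-specification with a consequence under either reading. Taken literally, section 17.1 tests an average over visits and dilutes the one-month comparison of Aim 1. Completed with a time-by-arm term and a constant-variance random intercept, it understates the visit 6 standard error if weight drifts.

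A reader might infer that the plan doubles the false-positive rate. The documents do not support that. A doubling needs a model the plan does not name and a noise-free random walk that no figure in the plan establishes. Across the structures examined, the understatement runs from 0% to about 29% and the type I error from 5% to about 17%, with 6% to 10% for a random walk with weighing noise. All of this assumes 10 per arm, a two-sided 5% level and no dropout. The point should be settled before analysis; it does not invalidate the design.

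**What to change.** State in section 17.1 that the primary analysis is percent weight change at visit 6, compared between arms by linear regression with t-based confidence limits. This matches Aim 1 and the endpoint in section 2.1, and it removes both problems.

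If all visits are modelled together, include a time-by-arm term, name the visit 6 contrast as primary, and use an unstructured covariance by visit with REML and Kenward-Roger degrees of freedom. An unstructured covariance without the interaction would still leave the visit 6 effect undefined. State also which weight is baseline, since section 10.2 points to screening.

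The cost is wording. No subjects, visits or measurements are added. The downside is a wider visit 6 interval than a random-intercept fit would give, by about 27% in the random-walk scenario.

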Subjects will come back within 2 weeks and will arrive after having fasted overnight (10 hours) at 7 to 7:30 am. They will then be randomized to either active tDCS or sham tDCS with block randomization (block size of 10). We will test urine pregnancy test to rule out pregnancy. Pregnant subject will be excluded from the study. We will also administer the three-factor eating questionnaire (Stunkard and Messick, 1985), which measures eating habits and attitudes toward food, weight and dieting, and a personality questionnaire, the Big Five (Costa and McCrae, 1989). We will evaluate cognitive responses to food with a 20-minute computerized task designed to engage the inhibitory control circuit when confronted with food stimuli, as well as engaging the other two components of executive function: working memory and cognitive flexibility. The task consists of 3 parts: a version of a Go/No-Go (GNG) task modified for food; an N-back memory task with food images, similar to a task used in a previous study; and a combined N-back and GNG task. In the food modified GNG task subjects have to press the space bar of a computer in response to pictures of low-calorie food, refraining from pressing when the pictures are of high-calorie food (25% of the time). In the N-back task, subjects will press the space bar when the picture displayed matches the picture displayed two images before. In the combined task, the subject will press the space bar when a picture of low-calorie food matches the picture displayed two images before, while refraining from pressing when a high-calorie food matches the picture displayed two images before.

Blood sample for BDNF and COMT gene test will be collected. We will also collect blood sample for plasma insulin and glucose level. We will download data from the continuous glucose monitor.

Subjects assigned to active tDCS group will receive 30 min of anodal tDCS delivered with a neuroConnVR DCSTIMULATOR device (neuroConn GmbH, Ilmenau, Germany), at a constant current of 2 mA (with a 30-second ramp at on- and offset) using two sponge electrodes soaked in a sterile 0.9% sodium chloride solution. The anode electrode will be placed over F3 (10–20 EEG system), with the cathode electrode placed over the contralateral supraorbital area, above the right eyebrow. This montage was used in a recent study that showed reduction of body weight and intake of soda and fat in a sample of obese subjects.

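### Section 17.1 uses baseline both as a response and as a covariate, without defining the treatment contrast or how covariates enter, so the baseline-imbalance analysis may adjust nothing or estimate a diluted effect

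*Combined protocol and SAP*

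**What the plan says.** The whole analysis plan is one paragraph in Section 17.1.

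- Model: "Generalized linear mixed model will be applied to compare the difference in weight, average amplitude of glucose excursion curve", and likewise for meal count, HOMA-IR, reaction time and percentage correct.
- Terms: "Predicting variables include time in the study (baseline, visit 5 and visit 6) and type of intervention (active tDCS vs sham". No time-by-intervention term, random effect or covariance structure is given.
- Sensitivity: "Sensitivity analysis will be performed to evaluate baseline imbalance, outliers, protocol violation, and missing data".
- Covariates: "The proposed covariants to be evaluated for baseline imbalance includes age, gender, COMT and BDNF gene status, baseline weight, baseline HOMA-IR", continuing with "baseline average amplitude of glucose excursion curve, baseline average daily meal count, baseline reaction time and percentage correct response". The plan does not say whether these enter as main effects, as covariate-by-time terms, or only in a table comparing the arms at baseline.

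The aims in Section 1.1 compare change over one month between arms. Section 2.0 defines the endpoints as changes: "Primary endpoints: change in weight, measured as a percentage of baseline body weight". Section 17.1, however, models weight.

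**The concern.** Each modelled outcome's baseline value appears twice: as the first response in the model and as a candidate covariate. A baseline value cannot do useful adjustment work on the change from baseline if it is also part of the response and enters with the same coefficient at every visit. The plan leaves open which quantity is the treatment effect, and the two most direct readings of its text both go wrong.

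With 20 subjects, sizeable chance differences between arms are to be expected, so this sensitivity analysis is likely to be relied on. If it cannot move the change contrast, the report will describe the result as robust to imbalance when nothing was tested. The trial would also give up precision that its baseline measurements could supply at no extra cost.

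**Working it through.** The plan states no alpha, effect size, SD or correlation, so it has no figure of its own to reproduce. The inputs are:

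- N = 20 (Section 5.1) and two arms. For allocation, Section 10.1 says "They will then be randomized to either active tDCS or sham tDCS with block randomization (block size of 10". A 1:1 ratio is not stated; 10 per arm is assumed.
- Time levels: baseline, visit 5, visit 6 (Section 17.1).
- The baseline-to-follow-up correlation r is assumed, range 0.3 to 0.6, with equal SDs.
- Assumptions for the kilogram simulations (40 trials): baseline SD 15 kg, imposed arm difference 8 kg, follow-up-on-baseline slope 0.9, residual SD 2 kg, true visit 6 effect -2 kg.

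**1. Arm-by-time model, covariates as main effects.** A subject-level covariate x with one coefficient b adds bx to all three visits. In (visit 6 - baseline) it contributes bx - bx = 0, so with complete data the contrast is the raw difference in change scores. In all 40 complete-data trials, the contrast with and without own baseline, and with and without age, differed by 0.00000. A generalised least squares check on one data set gave -2.00983 kg with and without these covariates, under compound symmetry (rho 0, 0.5, 0.95) and an unstructured covariance. With a few missing visits, adding own baseline moved it by 0.12 kg on average and at most 0.35 kg. The cancellation is then approximate.

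**2. Only the listed terms, time plus intervention.** With a random intercept and complete data, the intervention coefficient is the arm difference averaged over all three visits.

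- Adjusted for own baseline, it estimates (0 + effect at visit 5 + effect at visit 6)/3. A constant effect of 1 gives 2/3 = 0.67; an effect of 1 at visit 6 only gives 1/3 = 0.33. A simulation of 4,000 trials (10 per arm, r = 0.6) returned 0.67 and 0.33. ANCOVA at visit 6 gave 1.00 in both cases.
- Unadjusted, it also carries the baseline difference. In the kilogram simulations the mean coefficient was +6.34 kg, the wrong sign, and -1.03 kg after adjustment. The realised mean baseline difference was 5.02 - (-2.88) = 7.90 kg (visit 6 arm difference minus change contrast). Its averaged contribution is 7.90 x (1 + 0.9 + 0.9)/3 = 7.37, and 7.37 - 1.03 = 6.34.

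**3. Baseline acting on follow-up only.** Adding baseline-by-time terms, which with complete data is identical to ANCOVA at visit 6, moved the mean visit 6 effect from -2.88 to -2.08 kg against a true -2. The shift is (1 - 0.9) x 7.90 = 0.79 kg, matching 2.88 - 2.08 = 0.80 up to rounding and simulation error. The largest shift in a single trial was 2.41 kg.

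**4. Size in SD units.**

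- SD of the chance baseline difference: sqrt(2/10) = 0.45 SD.
- Shift of the change contrast given a baseline difference D: -(1 - r)D. For D = 0.45 SD this is 0.4 x 0.45 = 0.18 SD at r = 0.6 and 0.7 x 0.45 = 0.31 SD at r = 0.3.
- Variance of ANCOVA relative to the change score: (1 - r^2)/[2(1 - r)] = (1 + r)/2, times 1 + 1/(18 - 2) = 1.0625 for estimating the slope with 18 within-arm degrees of freedom. At r = 0.6: 0.80 x 1.0625 = 0.85. At r = 0.3: 0.65 x 1.0625 = 0.69 (simulated 0.70). The saving is about 15% to 30%.

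**5. Primary endpoint.** Percent change is zero at baseline for everyone, so baseline cannot usefully be a response level on that scale, and adding baseline weight does adjust: -2.53 to -1.94 percentage points in the same simulations. That movement comes from the imposed 8 kg difference and the 0.9 slope. It shrinks towards zero as the slope approaches 1, which is plausible for weight over about a month.

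**The case against.** A reader might infer that the planned sensitivity analysis must return the unadjusted effect and can never reveal an imbalance. The documents do not support that. The cancellation needs a time-by-intervention contrast, main-effect covariates and complete data, and Section 17.1 states none of these. Section 20.3 keeps partial records of withdrawn subjects, so complete data cannot be presumed. Under the listed terms the coefficient moves a great deal when baseline is added, and so does the visit 6 arm difference in the interaction model (+5.02 to -2.36 kg). Covariate-by-time terms would adjust properly. The wording also allows a direct comparison of arms at baseline, which would show an imbalance, although it would not correct the estimate.

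A reader might also infer that covariates will be selected on observed imbalance, or that the whole list will enter at once. The plan names ten proposed covariates and states neither.

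The strongest counter-argument is that, under randomisation, the unadjusted change contrast is unbiased over repeated trials with a valid type I error. What remains is conditional bias and efficiency, in a pilot that says "This is a pilot study, so we are not able to estimate sample size", and least of all for the primary endpoint. That stands, and it limits the weight of the point.

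It does not remove the point. That a coefficient moves does not make it the right quantity: the additive model's coefficient includes a visit before any stimulation was given. A plan under which an unchanged result may be pure algebra needs its contrast and covariate terms written down.

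**Conclusion.** The point holds as a conditional one. Section 17.1 does not define the treatment contrast or how baseline covariates enter. Under one natural reading the change contrast is not adjusted for imbalance at all; under the other, the estimate mixes in baseline differences or is diluted to two-thirds of a constant effect (one-third of an effect seen only at visit 6).

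The practical loss is a shift of about 0.18 to 0.31 SD after a typical chance imbalance and about 15% to 30% of variance. Both rest on an assumed 10 per arm and assumed r of 0.6 to 0.3. They apply mainly to HOMA-IR, glucose amplitude, meal count and the cognitive measures, and little to percent weight change. The kilogram figures depend on the simulation inputs; the cancellation and the two-thirds and one-third factors do not. This is a worthwhile and nearly free improvement, not a flaw that makes the randomised comparison invalid.

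**What to change.** In Section 17.1:

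- Take baseline out of the response. Model the visit 5 and visit 6 values (percent change for weight, to match Section 2.0) on arm, visit, arm-by-visit and that outcome's own baseline by visit.
- Name the visit 6 arm contrast as the treatment effect.
- Where an outcome has no visit 5 value, use ANCOVA at visit 6. Section 10.2 lists meal counts only at visits 1 and 6.
- Run any adjustment for age, sex or genotype one at a time in this model, labelled supportive.

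A model that keeps baseline as a response but constrains the arm means to be equal at baseline is an acceptable equivalent. The cost is wording and about one degree of freedom per baseline slope fitted. No new data are needed.
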